Dopamine agonists such as pramipexole are efficacious and first-line FDA-approved treatments in low doses for primary (i.e., idiopathic) RLS ([name] et al., 2006, 2016). Dopamine agonists are also efficacious for secondary RLS associated with end-stage renal disease (Pellecchia et al., 2004), peripheral neuropathy (Bastia et al., 2015) and pregnancy (Dostal et al., 2013). A few published case reports suggest that dopamine agonists are also effective in opioid withdrawal-related RLS (Ghosh & Basu, 2014; Park et al., 2010, 2014), and it is not uncommon for opioid detoxification units to have dopamine agonists (e.g., ropinirole, pramipexole) on formulary to address RLS. FDA-approved dopamine agonists not only dramatically reduce core RLS symptoms of leg restlessness and dysesthesia but by this mechanism produce substantial improvements in sleep disturbance in both primary and secondary RLS ([name] et al., 2016). As opioid withdrawal is prominently characterized by sleeplessness (Oyefeso et al., 1997), which is thought to independently confer risk for relapse to opioid use (Beswick et al., 2003), treatment of protracted opioid withdrawal related RLS may also improve sleep in this cohort.

We hypothesize that effective treatment of RLS symptoms with pramipexole is an effective treatment for RLS symptoms in OUD patients during post-detox clinical stabilization. Further, we

hypothesize that treatment of RLS in this context will also improve overall symptoms of opioid withdrawal as assessed by the SOWS. As exploratory aims, we also hypothesize that treatment of RLS symptoms will (i) improve subjective sleep quality and duration and reduce self-reported sleep disruption, and (ii) contribute to longer stays in the inpatient OUD step-down stabilization treatment facility. Retention in treatment – longer stays in the facility with its multi-dimensional treatment strategy options - is highly correlated with success in OUD outcomes. (Fleury et al., 2016).

II. SPECIFIC AIMS

Primary Aim:

• To determine whether pramipexole will have significantly greater effect than placebo in reducing RLS symptoms in OUD patients immediately following acute opioid withdrawal during post-detox clinical stabilization

Secondary Aim:

• To determine whether pramipexole will have significantly greater effect than placebo in reducing self-reported opioid withdrawal symptoms in OUD patients immediately following acute opioid withdrawal during post-detox clinical stabilization.

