Exploratory Aims:

- To determine whether pramipexole will have significantly greater effect than placebo for self-reported sleep metrics (e.g., quality, disturbance, sleep latency and duration) in OUD patients immediately following acute opioid withdrawal during post-detox clinical stabilization.
- To determine whether OUD patients on pramipexole will stay in the post-detox clinical stabilization unit longer than those on placebo. This will enable a higher rate of successful referral to after-care than those on placebo.

III. SUBJECT SELECTION

The following lists the inclusion/exclusion criteria for prospective participants.

Inclusion Criteria:

- 1. Men or women of any ethnic origin.
- 2. Written informed consent is obtained
- 3. Speaks and writes in English
- 4. A willingness and ability to comply with study procedures.
- 5. Age 18–75 years

- 6. Patients with diagnosed OUD who have undergone primary detoxification for their OUD in any detox facility, have been transferred to the Gavin Clinical Stabilization Service (CSS), and have some persistent opioid withdrawal as indicated by a SOWS>1 on Day 1
- 7. Diagnosis of RLS from the Hening Telephone Diagnostic Interview (HTDI) with subsequent confirmation by clinical interview conducted by a study physician (e.g., [name], [name])
- 8. International Restless Legs Syndrome Severity Scale (IRLS) Symptoms subscale score of >11 for three consecutive days prior to randomization. Participants who miss one day of questionnaires prior to randomization may be included if the IRLS subscale score is >11 for each day questionnaires are completed.

Exclusion Criteria:

- 1. Pregnant. Gavin Foundation staff perform pregnancy tests upon admission to the CSS.
- 2. Participants with active or unstable major psychiatric disorder other than OUD, who, in the investigators' judgement, require further treatment
- 3. Neurological disorder or cardiovascular disease raising safety concerns about use of pramipexole and/or judged to interfere with ability to assess efficacy of the treatment
- 4. Medical instability considered to interfere with study procedures
- 5. Stage 3, 4, or 5 renal insufficiency
- 6. Participation in this study on a previous admission to the CSS

IV. SUBJECT RECRUITMENT AND ENROLLMENT

Methods of recruitment and procedures for informed consent:

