Screening Run-In (3 days): The participant will receive daily email links to an online sleep diary and three questionnaires: the IRLS subscale, SOWS, and an opioid craving visual analog scale. Baseline subjective sleep measures will be determined from this 3-day period.

RANDOMIZATION VISIT (VISIT 3) AND TREATMENT PERIOD:

A more thorough medical history will be collected at the Randomization Visit, along with demographic information. At this visit, the 3-day sleep diary and questionnaire results will be reviewed for final eligibility before the participant is randomized to treatment.

Eligible participants will be randomized in a 1:1 ratio to 10 days of placebo or pramipexole. Pramipexole will be started at 0.25 mg nightly for the first 3 days. On day 3, a study physician will call the participant over the phone or on video to inquire about efficacy and adverse events (Visit 4). Visit 4 may occur on day 4 or 5 if the study physician is unable to meet on day 3. If the 0.25-mg dose is well tolerated but not effective, the dose can be increased to 0.5 mg.

Participants will receive medication from the Gavin Foundation staff and will complete the online sleep diary and questionnaires every day (see the Table of Procedures below for the exact schedule). Gavin Foundation staff will direct participants to the secure computer on which they can complete the sleep diary and questionnaires.

FINAL STUDY VISIT (VISIT 5):

On Day 10, participants will meet with a study physician. The physician will assess the participant on the Clinical Global Impression-Improvement (CGI-I) scale and will also inquire about any adverse events experienced. If a participant is discharged from the Gavin Foundation CSS before Day 10, study staff will attempt to perform Visit 5 before his or her departure from the facility.

Compensation:

Participants will be remunerated. Any earnings will be loaded onto a debit card, which will be given to the participant when he or she leaves the Gavin Foundation CSS.

Participants will be paid based on completion of sleep diaries and questionnaires after receiving study drug.

The payment schedule is as follows:

- \$5/day for filling out diaries and questionnaires on the 10 days on study drug
- \$25 for fully completing the study (i.e. spending 10 days on the study drug and completing 10 days of diary entries)

The total possible compensation is \$75.

[figure not shown]

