This research has potential benefits to society: this study may help other people with OUD and RLS symptoms by adding to the knowledge about this drug, and whether it is a beneficial treatment.

IX. BIOSTATISTICAL ANALYSIS

Analysis of all study data will be conducted by [name], [name], and [name] or another statistician at Partners Healthcare hospitals. All study personnel and participants will remain blinded to treatment assignment, including staff entering study data. Only the hospital Research Pharmacist who generates the randomization code and [name] who will conduct the interim analysis will be unblinded to treatment assignment. The final database will not be unblinded to study staff until all study data are complete and a medical and scientific review by [name] is conducted.

Overview of analytic plan:

We will conduct an interim analysis to probe the futility of the study. We will use the data obtained to date to estimate the effect of randomized treatment group on two outcomes (primary outcome: IRLS score; secondary outcome: SOWS). We will then use this estimate to determine the sample size necessary to detect this effect. To protect the blind, a statistician ([name]) who is not involved in the day-to-day running of the study, will conduct the analyses.

We will perform both intent-to-treat (ITT) analyses (including all patients who received one dose of study medication and complete one assessment post-randomization) and per protocol analyses (including participants with 10 days of evaluable data). Distributions of the outcomes will be examined and data transformation will be applied to satisfy the normality assumptions.

We will analyze data in several ways: comparison of change from randomization to end of Day 5; comparison of change from randomization to end of Day 10; and using all daily values (i.e., longitudinal analyses). The two groups are drug and placebo.

Study endpoints:

The primary outcome (IRLS score) and all secondary and exploratory measures are continuous variables. We will modify the IRLS in two ways: (i) only the symptoms subscale will be employed (only items 1, 2, 4, 6, and 8 will be included); and (ii) the questions will be modified to include symptoms for only the last 24 hours rather than for the previous 7 days. Primary

analyses will focus on the difference in the change in IRLS subscale from randomization to Day 5 and from randomization to Day 10 between the two groups.

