The key secondary variables are the difference from randomization to Day 5 and from randomization to Day 10 in SOWS.

Exploratory analyses will similarly focus on the differences from randomization to Day 5 and from randomization to Day 10. These endpoints include:

- 1. Subjective total sleep time
- 2. Subjective sleep latency
- 3. Subjective time awake after sleep onset
- 4. Depressive (PHQ-9) and anxiety (GAD-7) symptoms
- 5. Time spent in the Gavin CSS

STATISTICAL METHODS

Interim analysis:

(i) Two-sample t-tests will be applied to estimate the effect of randomized treatment group on IRLS subscale score, for the subjects with post-randomization data to date. Using the estimated treatment effect, we will conduct a power analysis to determine the sample size necessary to detect this effect. (i) Two-sample t-tests will be applied to estimate the effect of randomized treatment group on SOWS, for the subjects with post-randomization data to date. Using the estimated treatment effect, we will conduct a power analysis to determine the sample size necessary to detect this effect.

Primary analysis:

(i) Two-sample t-tests will be applied to compare the change in IRLS subscale from randomization to Day 5 and from randomization to Day 10 between the two groups. (ii) Linear mixed-effects models will also be applied to the longitudinally measured IRLS subscale with entry of covariates that correlate with changes in primary endpoints as required (e.g., age, sex, and at-randomization levels of IRLS severity, and SOWS). Subjective sleep measures from the sleep diary for every night of data collection will also be added as potential covariates to the linear mixed-effects models.

Secondary Analysis:

(i) Two-sample t-tests will be applied to compare the change in SOWS from baseline to Day 5 and to Day 10 between the two groups. (ii) Linear mixed-effects models will also be applied to longitudinally measured SOWS with entry of covariates that correlate with changes in primary endpoints as required (e.g., age, sex, and at-randomization levels of IRLS severity, and SOWS).

Subjective sleep measures on every night of data collection will also be added as potential covariates to the linear mixed-effects models.

Exploratory Analyses:

Linear and generalized linear mixed-effects models will be applied to compare changes in the self-reported sleep metrics (e.g., quality, disturbance, sleep latency and duration) across the nights of study and between the groups.

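### On-treatment sleep-diary measures may enter the IRLS and SOWS mixed models as covariates, and the treatment coefficient would then not be the randomized treatment effect

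*Combined protocol and SAP*

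**What the plan says.** The Primary analysis paragraph (Statistical Methods) has two parts: (i) two-sample t-tests of IRLS subscale change to Day 5 and Day 10, and (ii) linear mixed-effects models for the longitudinal subscale "with entry of covariates that correlate with changes in primary endpoints as required". The examples given for (ii) are age, sex, and IRLS and SOWS at randomization. The next sentence reads: "Subjective sleep measures from the sleep diary for every night of data collection will also be added as potential covariates". The Secondary Analysis paragraph does the same for SOWS: "Subjective sleep measures on every night of data collection will also be added as potential covariates".

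Four other places bear on this:

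- **Diary timing.** During treatment, participants "will complete the online sleep diary and questionnaires every day" (Overview of Study Procedures). The Table of Procedures marks the diary on each of Days 1 to 10.
- **Baseline sleep.** The Screening Run-In paragraph says: "Baseline subjective sleep measures will be determined from this 3-day period". The covariate sentences do not refer to this baseline.
- **Expected effect on sleep.** The Background says that dopamine agonists relieve RLS and "by this mechanism produce substantial improvements in sleep disturbance in both primary and secondary RLS". An exploratory aim is to determine whether "pramipexole will have significantly greater effect than placebo for self-reported sleep metrics", and diary sleep measures are listed exploratory endpoints.
- **Recall period.** For the IRLS, "the questions will be modified to include symptoms for only the last 24 hours" (Study endpoints).

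The plan does not say which mixed model, with or without sleep, gives the treatment effect. It does not mark a sleep-adjusted model as a mediation or sensitivity analysis.

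**The concern.** A covariate measured before randomization cannot be changed by treatment, so adjusting for it leaves the treatment effect intact and usually sharpens it. A covariate measured on treatment has no such protection. If the drug changes sleep, comparing the arms at equal sleep removes part of the drug's effect from the comparison. This is so whether sleep lies on the path from drug to symptoms or follows from symptom relief, as the Background suggests. Because the IRLS now covers 24 hours, a night's diary and the score beside it probably describe much the same period, which would make the overlap strong.

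The mixed model is listed under the primary analysis. It is also the listed analysis that naturally uses partial data from patients who leave early. The plan expects 88 randomized and 68 completing, a loss of 20/88 = 22.7%, so readers may well lean on it. If it showed a smaller effect than the t-test, they could not tell whether dropout or over-adjustment was the reason.

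**Working it through.** **1. Inputs from the plan (Power/Sample Size).** IRLS: 34 per arm, difference 6.3, SD of change 9.0, two-sided alpha 0.05, 80% power. SOWS: 34, difference 4, SD 6.0. The Table of Procedures gives six on-treatment IRLS readings, on Days 1, 3, 5, 7, 9 and 10.

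**2. The plan's own figure.** Exact two-sample t power at 34 per arm for 6.3/9.0 is 81.2%, so the stated 80% for IRLS reproduces. For SOWS (4/6.0) it is 77.3% (78.5% by the normal approximation), a little under 80%. Neither calculation involves covariates.

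**3. Assumptions not in the documents.** The within-arm correlation r between nightly sleep and IRLS is taken as 0.3, 0.5 or 0.6. The intraclass correlation (ICC, the persistence of a patient's values over days) is 0.5 for IRLS and for the sleep noise. Sleep enters the model on the same day as the score. The SD of 9.0, which the plan gives for the change, is used as the SD of each reading.

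**4. Closed form when sleep follows symptoms.** Let sleep = −r × (IRLS/9.0) + √(1−r²) × noise, with noise of SD 1.

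- Within arm, the slope of IRLS on sleep is −9.0r.
- A 6.3-point fall in IRLS raises sleep by 6.3r/9.0.
- Holding sleep constant removes 9.0r × 6.3r/9.0 = 6.3r² points, which leaves 6.3(1−r²).

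**5. Simulated mixed model.** Random intercept, REML, treatment and day effects, 600 replicates per setting.

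| r | 6.3(1−r²) | Without sleep | With nightly sleep | Loss |
|---|---|---|---|---|
| 0.3 | 5.73 | 6.35 | 5.79 | 9% |
| 0.5 | 4.73 | 6.27 | 4.71 | 25% |
| 0.6 | 4.03 | 6.32 | 4.05 | 36% |

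Setting both ICCs to 0.3 or to 0.7 changes these losses by no more than about one percentage point. At r = 0.5, a sleep-noise ICC of 0.2, 0.5 or 0.8 gives a loss of 19%, 25% or 40%.

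**6. The opposite causal order.** Here part of the 6.3 points runs through sleep (120 replicates). With 1.5, 2.4 or 3.0 points through sleep, the sleep-adjusted coefficient is 4.8, 3.9 or 3.4, against 6.3 − 1.5 = 4.8, 6.3 − 2.4 = 3.9 and 6.3 − 3.0 = 3.3 expected. Adjusting for baseline sleep instead gives 6.3 to 6.4, so the effect is preserved.

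**7. When the loss vanishes or reverses.** If sleep correlates with IRLS within arm but the drug does not move it, the adjusted coefficient is 6.31 to 6.37, so nothing is lost. If the drug worsens sleep by 0.3 SD, the expected value is 6.3 + 9.0 × r × 0.3 = 7.1, 7.7 and 7.9. The simulation gave 7.09, 7.67 and 7.98.

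**8. SOWS.** Scaling by the same factor, 4(1−r²) = 3.64, 3.00 and 2.56. At r = 0.5 the 19% to 40% range gives 4 × 0.81 = 3.24 down to 4 × 0.60 = 2.40.

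**The case against.** The strongest reply is that the unadjusted t-tests carry the trial. The plan says its primary analyses focus on change to Day 5 and Day 10, it powers both aims on a t-test, and it adds the mixed models as a further analysis in a self-described pilot. That is correct and limits the consequence. It does not remove the defect, because the mixed model is still listed under the primary analysis and the plan does not say which version of it estimates the effect.

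Second, the sleep measures are only *potential* covariates, and the correlation rule sits in the preceding sentence, where every example is a pre-randomization variable. The criticised model might never be fitted. This too is fair, but no other entry criterion is stated. If that rule is applied, on-treatment sleep is likely to satisfy it for the very reason that it should be kept out.

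Third, the point values are weakly anchored. The correlations and persistence are assumed, the SD of 9.0 is borrowed from a change score, the outcome is a five-item subscale, and the SOWS values are scaled by formula. The form in which sleep would enter (same night, lagged or averaged) is unspecified. All of this stands: the percentages are illustrations, and the two causal structures agree on direction, not on one figure.

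Finally, if sleep follows symptom relief, calling the adjusted model a mediation analysis would mislead. That is a sound caution on labelling.

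**Conclusion.** The concern holds. As written, the plan allows post-randomization sleep into the IRLS and SOWS mixed models, although the protocol names sleep as something treatment should change and as an outcome in its own right. The treatment coefficient from such a model is not the randomized treatment effect.

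Under the protocol's own hypothesis the expected direction is attenuation: about 9% to 36% for correlations of 0.3 to 0.6, and 19% to 40% at 0.5 as the persistence of sleep varies. These sizes rest on assumed correlations. The two estimates would coincide if the drug did not affect sleep, and the bias would reverse if it worsened sleep. Shared causes of poor sleep and symptoms could add bias either way.

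The t-tests, the sample size and the futility interim are untouched. The point should be fixed, but it does not threaten the unadjusted primary comparison.

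**What to change.** Before the final database is unblinded, reword the covariate sentences in the Primary analysis and Secondary Analysis paragraphs:

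- Fix the covariates in the IRLS and SOWS efficacy mixed models to a prespecified pre-randomization list: age, sex, IRLS at randomization and SOWS at randomization, all already named there. Mean run-in diary sleep, which the protocol already defines as baseline, may be added. Restricting sleep to the run-in cures the defect described here. Fixing the whole list also ends covariate selection by observed correlation with endpoint change.
- Remove post-randomization sleep from these models and state that they, without on-treatment sleep, give the longitudinal treatment effect.
- Label any model with on-treatment sleep exploratory. Call it a mediation analysis only with the assumed causal order stated.

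The cost is a few sentences. No data, visits or patients are added, and nightly sleep remains an exploratory outcome.

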Linear and generalized linear mixed-effects models and survival-based analyses will be applied to compare the number of days patients continue in CSS treatment between the two groups.

Power/Sample Size:

Power calculations are based on Specific Aims 1 and 2 detailed below. There are insufficient published or unpublished data to perform them on exploratory analyses (detailed above). Meta-analyses of RLS clinical trials indicate that placebo effects using the IRLS are strongly related to the duration of these trials (Fulda et al., 2008). Therefore, we are basing our calculations on short-term trials, similar to our study design, for pramipexole in RLS using abbreviated RLS symptom scales (e.g., Oertel et al., 2007; Manconi et al., 2007, 2012)

Aim 1: The primary outcome is the change in IRLS scale from baseline to Day 10. Using the Oertel et al. (2007) data as reference, with n=34 for each group, we will have 80% power to detect a 6.3 points difference in the change of IRLS scale (with a common standard deviation of the change of 9.0) with a two-sided two-sample t-test at alpha=0.05 level. A change of 3 is considered a clinically meaningful difference from placebo (Allen et al., 2013).

Aim 2: The primary outcome is the change in SOWS. Using the Dunn et al. (2017) data as reference, with n=34, we will have 80% power to detect a 4 points difference in the change of SOWS (with a common standard deviation of the change of 6.0) with a two-sided two-sample t-test at alpha=0.05 level.

Therefore, our plan is to enroll 160 people in a 1:1 drug:placebo ratio in order to randomize 88 patients with OUD and have 68 participants complete the 10-day trial. With approximately 16 patients per week admitted to the CSS with opioid use disorder, and an RLS prevalence of 50% in this context, we do not anticipate any difficulty enrolling to our target sample size for the trial within a 20-month enrollment period.

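### Aim 2 is powered as one SOWS test at two-sided 0.05 but analysed on Day 5 and Day 10 with no decisive day, so its false-positive rate is about 7% to 10%

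*Combined protocol and SAP*

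**What the plan says.** All references are to the combined protocol and SAP.

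- **Section II, Secondary Aim**: "To determine whether pramipexole will have significantly greater effect than placebo in reducing self-reported opioid withdrawal symptoms in OUD patients". The comparison with placebo is worded as for the primary aim, and exploratory aims are listed separately.
- **Section IX, Study endpoints**: "The key secondary variables are the difference from randomization to Day 5 and from randomization to Day 10 in SOWS".
- **Section IX, Statistical Methods, Secondary Analysis**: "Two-sample t-tests will be applied to compare the change in SOWS from baseline to Day 5 and to Day 10 between the two groups". A longitudinal mixed model for SOWS is planned as well.
- **Section IX, Power/Sample Size, Aim 2**: change in SOWS is called the primary outcome of this aim, with no day given. The claim is "we will have 80% power to detect a 4 points difference in the change of SOWS", and the calculation is made "with a common standard deviation of the change of 6.0" and "with a two-sided two-sample t-test at alpha=0.05 level". The Aim 1 paragraph, by contrast, names Day 10 for IRLS.

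SOWS is ranked as secondary to IRLS in several places. No section gives an alpha split, a testing order, or a condition that IRLS must be significant before SOWS is claimed. The 0.05 level appears only in the two power statements; the analysis section sets no level for any test.

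**The concern.** Aim 2 has its own power calculation at 0.05, so it is meant to be answered by a test. A reader needs to know which result answers it. As written, there are two candidate t-tests and no rule for choosing between them. A significant difference on either day could be presented as meeting the aim, and the day could be chosen after the data are seen. The error rate behind a claim of reduced withdrawal would then exceed the only level the document states. The power statement would also describe a different procedure from the one carried out, because it allows for one test and not two.

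**Working it through.** **Inputs.** From Power/Sample Size, Aim 2: difference 4, SD of change 6.0, n = 34 (read as per group, as in Aim 1), two-sided alpha 0.05. From Study endpoints and Secondary Analysis: two test days. The documents give no correlations, so those below are assumptions, shown as ranges. Test statistics are treated as normal unless stated.

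**1. The plan's own figure.** Noncentrality = (4/6.0) × √(34/2) = 2.749. Normal approximation: power = Φ(2.749 − 1.960) = 78.5%. The noncentral t with 66 df gives 77.3%. The stated 80% is roughly reproduced (80% needs 36 per group by the normal formula, 37 by t). It is therefore the power of one test using the whole 0.05. At 0.025 per test, power with 34 per group would be 69.4% (normal) or 67.5% (t).

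**2. False-positive rate for Aim 2 if either day counts.** With no drug effect and each test at 0.05:

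Two-sided: P(either) = 0.05 + 0.05 − P(both significant).

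Benefit only: P(either) = 0.025 + 0.025 − P(both significant in favour of pramipexole).

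| Assumed between-day correlation | Two-sided | Benefit direction |
|---|---|---|
| 0 | 9.75% | 4.9% |
| 0.3 | 9.5% | 4.8% |
| 0.5 | 9.1% | 4.5% |
| 0.7 | 8.3% | 4.2% |
| 0.8 | 7.8% | 3.9% |
| 0.9 | 7.0% | 3.5% |

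At correlation 0.5, for example, P(both) = 0.0093, so 0.10 − 0.0093 = 0.0907. Whatever the correlation, two tests cannot exceed 0.05 + 0.05 = 10% two-sided, or 5% in the direction of benefit. The single-test references are 5% and 2.5%. The count covers the two t-tests in one analysis set; it leaves out the mixed model and the per-protocol repeat.

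**3. Adding IRLS Day 10.** This is the chance of at least one two-sided false positive among IRLS Day 10, SOWS Day 5 and SOWS Day 10. The correlation between IRLS Day 10 and SOWS Day 5 is set to the product of the other two.

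| SOWS between-day correlation | IRLS–SOWS 0.3 | 0.5 | 0.7 |
|---|---|---|---|
| 0.5 | 13.4% | 12.9% | 12.2% |
| 0.7 | 12.7% | 12.2% | 11.4% |
| 0.8 | 12.2% | 11.7% | 10.9% |

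If all three were independent it would be 1 − 0.95³ = 14.3%.

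**4. What the possible rules do.**

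- *One named SOWS day at 0.05*: the rate is 5% two-sided and 2.5% for benefit. Power stays as in step 1.
- *Both days at 0.025 each*: the rate is at most 5%, but 80% power needs 43 (normal) or 45 (t) per group. That is 2 × 43 = 86 to 2 × 45 = 90 completers, against the 68 planned.
- *SOWS Day 10 tested only after a significant IRLS Day 10*: with the planned effects (6.3/9.0 and 4/6.0) and 34 per group, the chance that both are significant is 65.6%, 67.8% and 70.3% at assumed IRLS–SOWS correlations of 0.3, 0.5 and 0.7. SOWS tested without that condition has about 77%.

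**The case against.** The trial is titled a pilot, and SOWS is labelled secondary throughout, so formal multiplicity control may seem more than it needs. Calling SOWS the primary outcome of Aim 2 can be read simply as the main measure for that aim. Day 10 is arguably implied, because the sample size is set by 68 patients completing the 10-day trial. These points lower the weight of the concern. They do not supply a rule: the endpoint section gives both days equal standing, and Aim 1 shows that the authors named a day when they meant one.

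The plan also never says that each day is tested at 0.05. That is the natural reading of its silence, and the figures depend on it.

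Two stronger readings are tempting and should be resisted:

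- **A reader might infer that false withdrawal claims run at about 13%.** That figure belongs to the three-test family in step 3, which includes trials where only IRLS is falsely significant and no withdrawal claim arises. It also counts results against pramipexole.
- **A reader might infer that a SOWS claim after a non-significant IRLS test contradicts the protocol's rationale.** Section I does "hypothesize that treatment of RLS in this context will also improve overall symptoms of opioid withdrawal as assessed by the SOWS". But a non-significant IRLS test does not show that RLS went untreated: at the planned effect and 34 per group, IRLS power is about 81%, so roughly 19% of trials with a true effect of that size would miss it. The missing condition on IRLS raises the error rate across the two aims together, not the SOWS rate alone.

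**Conclusion.** The point holds for Aim 2 itself. Testing SOWS on two days with no decisive day puts its two-sided false-positive rate at 1.4 to 1.95 times the stated level (7.0/5 to 9.75/5). The ratio is about the same in the direction of benefit (3.5/2.5 to 4.9/2.5). This rests on three assumptions: significance on either day would count, each test is read at 0.05, and the between-day correlation lies between 0 and 0.9.

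With IRLS Day 10 included, the chance of at least one false positive is about 11% to 13% for SOWS between-day correlations of 0.5 to 0.8 and IRLS–SOWS correlations of 0.3 to 0.7. That describes the two aims jointly.

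For a secondary aim in a pilot this is a moderate defect. It should be corrected before unblinding, because a day chosen afterwards would not be credible.

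**What to change.** **Main change.** In Study endpoints, Secondary Analysis, and Power/Sample Size (Aim 2), name change in SOWS from randomization to Day 10, at two-sided 0.05, as the sole test of Aim 2. In the Aim 2 paragraph, call it the key secondary outcome instead of the primary outcome. Report SOWS Day 5 and the SOWS mixed model as supportive estimates with 95% confidence intervals and no significance claim.

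*Cost*: wording only. Sample size and single-test power do not change, and Day 10 fits the planned 68 completers. The small downside is that an effect seen only at Day 5 cannot be claimed.

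**Optional further step**, if the sponsor wants 5% control across both aims: test SOWS Day 10 only if IRLS Day 10 is significant, and otherwise report SOWS descriptively. This first requires IRLS Day 10 to be fixed as the single primary test, since Study endpoints and Primary analysis currently give Day 5 and Day 10 equal standing for IRLS.

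*Cost*: Aim 1 loses no alpha or power, but the chance of a claimable SOWS result falls from about 77% to about 66% to 70%. The sponsor should weigh that loss; the main change does not depend on it.
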